2.0 TRIAL DESIGN

This is a non-randomized Phase 2 trial using the Simon's optimal two-stage design. In the first stage, 13 eligible patients will enroll. If there are 2 or fewer patients with response (CR or PR), the study will be suspended for lack of sufficient efficacy. Otherwise, 16 additional patients will be accrued for a total of 29 patients. An accrual period of 24 months and follow-up period of 12 months are anticipated. More than 29 patients may be screened and/or enrolled depending on screen fails and dropouts before starting treatment.

Figure 2.1. Study schema

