7.3 Duration of therapy

Patients will begin cabozantinib and pembrolizumab concurrently. Patients may continue study therapy until unequivocal disease progression, unacceptable drug-related toxicity, or subject withdrawal. If one drug needs to be permanently discontinued due to toxicity, the other agent may be continued. Interval dosing interruption/delay of either or both agents is allowed for AEs (see Section 9.0).

Treatment beyond progression with cabozantinib and/or pembrolizumab (depending on patient tolerance) will be allowed based on meeting pre-specified criteria and after discussion with the study PI (see Section 12.1).

Patients may be treated up to a maximum of two years from the time of treatment initiation.

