9.4 Dose levels of cabozantinib

Cabozantinib must be started at 40 mg orally once daily and reduced to 20 mg orally once daily (minimum dose) for toxicity. Cabozantinib must be discontinued permanently if the minimal dose is not tolerated. Re-escalation to 40 mg once daily is not recommended, but may be allowed if there is a reason to believe that the patient will tolerate this dose after discussion with the PI.

Table 9.4.1. Dose levels for cabozantinib		
Dose Adjustment Level	Oral Dose	Frequency
0 (starting dose)	40 mg	Once daily
-1	20 mg	Once daily
-2		Discontinue

9.5 Guidance on dose modification of cabozantinib and pembrolizumab for non-immune and immune toxicities

Both non-immune and immune-mediated toxicities may occur on study.

The sections below provide guidance on dose modifications for TRAEs, in addition to management recommendations for cabozantinib-specific toxicities discussed in Section 9.3. However, management

RG1007034

may differ from this guidance based on the clinical judgement of the investigator. In all patients, supportive care should be initiated to manage the AEs in addition to dose modification of study drugs.

For potential irAEs, please refer to the ASCO Clinical Practice Guidelines for Management of Immune-Related Adverse Events in Patients Treated With Immune Checkpoint Inhibitor Therapy.⁵⁸

If dose is interrupted for TRAEs, cabozantinib must be resumed within 4 weeks of last dose, and pembrolizumab must be resumed within 12 weeks of last dose. Resuming drugs beyond these time points must be discussed with the Study PI.

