13.1.2 Definitions of response

12.1.2.1 Evaluation of response of target lesions

Complete response (CR): Disappearance of all target lesions. Any pathological lymph nodes (whether target or non-target) must have a reduction in short axis to < 10 mm.

Partial response (PR): At least a 30% decrease in the sum target lesions, taking as reference the baseline sum diameters.

Progressive disease (PD): At least a 20% increase in the sum target lesions, taking as reference the smallest sum on study recorded since the treatment started, or the appearance of one or more new lesions. In

addition to the relative increase of 20%, the sum must also demonstrate an absolute increase of at least 5 mm.

Stable disease (SD): Neither sufficient shrinkage to qualify for PR nor sufficient increase to qualify for PD, taking as reference the smallest sum diameters since the treatment started.

12.1.2.2 *Evaluation of response of non-target lesions*

Complete response: Disappearance of all non-target lesions and normalization of tumor marker level. All lymph nodes must be non-pathological in size (< 10 mm short axis).

Incomplete response/stable disease: Persistence of one or more non-target lesion(s) and/or maintenance of tumor marker level above the normal limits.

Progressive disease: Appearance of 1 or more new lesions and/or unequivocal progression of existing non-target lesion(s).

13.1.3 **Evaluation of overall response**

The best overall response is the best response recorded from the start of the treatment until disease progression/recurrence (taking as reference the smallest measurements recorded since the treatment started to determine response and progression).

Target lesions	Non-target lesions	New lesion	Overall response
CR	CR	No	CR
CR	Non-CR/Non-PD	No	PR
CR	Not evaluated	No	PR
PR	Non-PD or not all evaluated	No	PR
SD	Non-PD or not all evaluated	No	SD
Not all evaluated	Non-PD	No	NE
PD	Any	Yes or No	PD
Any	PD	Yes or No	PD
Any	Any	Yes	PD

Subjects with a global deterioration of health status requiring discontinuation of treatment without objective evidence of disease progression at that time should be classified as having "symptomatic deterioration". Every effort should be made to document the objective progression even after discontinuation of treatment.

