17.0 STATISTICAL CONSIDERATIONS

17.1 Sample size calculation

The primary objective of this study is to evaluate the ORR in patients with advanced HCC treated with cabozantinib and pembrolizumab. This Phase 2 trial will be based on Simon's optimal two-stage design.

The null ORR is assumed to be 20%, which was the ORR (by RECIST v1.1) observed in the sorafenib-naïve group treated with nivolumab in the CheckMate 040 trial.⁸ Early phase data with lenvatinib and pembrolizumab as first-line treatment showed an ORR of 35% in the expansion phase and an ORR of 42% in the overall patient population (DLT evaluation and expansion phase) using mRECIST criteria.³⁸ Therefore, the null hypothesis that the true ORR is 20% will be tested against a one-sided alternative that the assumed-true ORR with the tested combination is 38% by RECIST v1.1. The target assumed-true ORR of 38% is believed to adequately represent the potential activity of cabozantinib and pembrolizumab.

Using Simon's optimal two-stage design, 13 patients will be accrued in the first stage. If there are 2 or fewer patients with response (CR or PR) (an observed rate of 15% or less), the study will be suspended for lack of sufficient efficacy. Otherwise, 16 additional patients will be accrued for a total of 29 patients. The null hypothesis (of an ORR of 20%) will be rejected if 9 or more patients have a tumor response (CR or PR) out of 29 patients (an observed ORR of at least 31%). This design yields a type I error rate of 0.10 and power of 80% when the true ORR is 38%.

An accrual period of 24 months and follow-up period of 12 months are anticipated. More than 29 patients may be screened and/or enrolled depending on screen fails or dropouts before starting treatment.

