17.2 Statistical methods

The primary endpoint is ORR per RECIST v1.1, while secondary endpoints include ORR by iRECIST, ORR and DCR by iRECIST, median PFS, and median OS. Only patients who have been on treatment with both cabozantinib and pembrolizumab concurrently for more than 42 days in the first 3 cycles (i.e. received treatment for two-thirds of the cycle) will be included in the analysis of the primary endpoint. Patients who have received any duration of study treatment will be evaluable for safety.

Binary endpoints will be summarized by percentages and associated confidence intervals. ORR will also be represented by a waterfall plot. The distribution for survival times will be estimated using the method of Kaplan-Meier; associated landmark time percentages and the median value will be based on this. Confidence intervals for median values will use the Brookmeyer-Crowley method. Any toxicity with at least 5% prevalence has at least an 77% chance of being observed among 29 patients.

For the exploratory objectives, archival or fresh tumors from all patients will be analyzed by IHC, the presence of specific immune cell subsets and protein marker expression, as well as the staining pattern and location within tumors will be described. The frequencies of immune cell subset will be obtained from flow cytometry at various timepoints, and cell changes from baseline to post-treatment timepoints will be averaged across patients. The association between immune cell, biomarker expression, gene expression signature, or cytokine level with ORR will be evaluated using Spearman correlation, where $p<0.05$ is considered significant.

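### The 42-day exposure rule in 17.2 drops treated patients from the primary ORR, so the evaluable number can fall below the 13 and 29 on which the Simon rule is fixed

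*Combined protocol and SAP*

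**What the plan says.** Section 17.2 limits the primary endpoint analysis: "Only patients who have been on treatment with both cabozantinib and pembrolizumab concurrently for more than 42 days in the first 3 cycles" are included. Three cycles are 63 days, so the threshold is two-thirds of that period. There is no exception for holds made for toxicity. The same section makes every treated patient evaluable for safety, but it defines no all-treated analysis of ORR.

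Other sections bear on who should be counted:

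- Section 17.1, objective: "The primary objective of this study is to evaluate the ORR in patients with advanced HCC treated with cabozantinib and pembrolizumab".
- Section 2.0: "In the first stage, 13 eligible patients will enroll". The trial stops at 2 or fewer responses; otherwise 16 more patients are accrued, for a total of 29.
- Section 17.1, final rule: the null "will be rejected if 9 or more patients have a tumor response (CR or PR) out of 29 patients".
- Section 17.1, extra enrolment: "More than 29 patients may be screened and/or enrolled depending on screen fails or dropouts before starting treatment".
- Section 13.1.3: "The best overall response is the best response recorded from the start of the treatment until disease progression/recurrence". No minimum exposure is attached.
- Section 9.5, after an interruption for treatment-related toxicity: "cabozantinib must be resumed within 4 weeks of last dose, and pembrolizumab must be resumed within 12 weeks of last dose".
- Section 7.3: "If one drug needs to be permanently discontinued due to toxicity, the other agent may be continued".

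**The concern.** Membership of the primary analysis set depends on what happens to a patient after treatment starts, and management that the protocol permits can remove a patient from it. A patient who stops one drug for toxicity by day 42, continues the other and later responds is not counted. A patient who dies or stops treatment by day 42 is left out instead of being counted as a failure. The resulting ORR describes patients who reached an exposure threshold, whereas 17.1 states the objective for patients treated with the combination.

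The rule also does not fit the design. The cutoffs of 2 and 9 were derived for 13 and 29 patients, and the plan says nothing about what to do with fewer evaluable patients. A response in an excluded patient does not count toward the 3 needed to pass stage 1 or the 9 needed to reject. An excluded non-responder leaves the denominator and raises the reported rate.

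**Working it through.** **Inputs.** From 17.1: null ORR 20%, alternative 38%, stage 1 n = 13 (stop at 2 or fewer responses), total n = 29 (reject at 9 or more), stated type I error 0.10 and power 80%. From 17.2: more than 42 concurrent days in 3 cycles. From 9.5: cabozantinib hold of up to 4 weeks. The number excluded is not in the documents; k = 1, 3 or 5 of 29 is assumed.

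**The plan's own figures.** P(reject) = Σ over x = 3 to 13 of P(X₁ = x) × P(X₂ ≥ 9 − x), with X₁ ~ Bin(13, p) and X₂ ~ Bin(16, p). This gives 0.0999 at p = 0.20 and 0.8044 at p = 0.38, so the stated design reproduces.

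**Exposure.** A full 28-day cabozantinib hold inside the first 63 days leaves 63 − 28 = 35 concurrent days, which is not more than 42. Any loss of 21 days or more (63 − 42 = 21) is enough to exclude a patient.

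**Case A: no replacement (as written), cutoffs 2 and 9 kept, exclusion unrelated to response.** The same formula with smaller n:

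| Excluded | Stage 1 / total, all lost after stage 1 | Type I error at 20% | Power at 38% | Stage 1 / total, some lost in stage 1 | Power at 38% |
|---|---|---|---|---|---|
| 0 | 13 / 29 | 0.100 | 0.804 | n/a | n/a |
| 1 | 13 / 28 | 0.084 | 0.774 | 12 / 28 | 0.758 |
| 3 | 13 / 26 | 0.057 | 0.695 | 12 / 26 | 0.684 |
| 5 | 13 / 24 | 0.036 | 0.591 | 11 / 24 | 0.574 |

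The chance of stopping at stage 1 when the true ORR is 38%, P(X₁ ≤ 2), is 0.077 with 13 evaluable, 0.107 with 12 and 0.148 with 11.

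**Case B: no replacement, all excluded patients are non-responders.** The response counts and the decision are unchanged. The reported rate for 9 responses is not:

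| Evaluable | ORR | Exact 95% CI |
|---|---|---|
| 29 | 31.0% | 15.3–50.8% |
| 28 | 32.1% | 15.9–52.4% |
| 26 | 34.6% | 17.2–55.7% |
| 24 | 37.5% | 18.8–59.4% |

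**Case C: excluded patients replaced up to 13 and 29 evaluable (not stated in the plan).** Let the true all-treated ORR be 20%, f = k/29 the excluded share and pe the response rate among those excluded. The evaluable rate is (0.20 − f × pe)/(1 − f). Putting it into the two-stage formula gives the chance of rejecting:

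| k | pe = 0 | pe = 0.20 | pe = 0.30 |
|---|---|---|---|
| 1 | 0.119 | 0.100 | 0.091 |
| 3 | 0.167 | 0.100 | 0.074 |
| 5 | 0.234 | 0.100 | 0.057 |

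Type I error exceeds 0.10 only if patients are replaced and those excluded respond at below 20%.

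**Counts against rates.** Section 17.1 also glosses the cutoffs as observed rates: 15% or less at stage 1 and at least 31% at the end. With fewer patients the two forms disagree. 2/12 = 16.7% stops by count but not by rate; 8/25 = 32% fails by count but passes by rate. The plan does not say which governs.

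**The case against.** The strongest argument is that the 38% target may itself rest on an evaluable denominator. Section 17.1 supports it with lenvatinib plus pembrolizumab data, and Section 1.2.5 describes that trial as 6 + 24 = 30 patients with an ORR of 42% (95% CI 23–63). Among denominators from 20 to 30, only 11/26 matches both the rate and an exact interval (23.4–63.1%). If 38% was meant for evaluable patients and 1, 3 or 5 of 29 are under-exposed non-responders, the all-treated ORR is 0.38 × (29 − k)/29 = 36.7%, 34.1% or 31.4%, and all-treated power is 0.76, 0.67 or 0.56. This stands as a cost, but it does not favour the current rule. Evaluable responders are a subset of all treated responders, so with the same patients and the same count cutoffs the all-treated rule never rejects less often than the present text without replacement. An inferred denominator in another trial also does not justify dropping treated patients when 17.1 states the objective for treated patients.

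Other points limit the size of the effect:

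- As written, false positives do not increase, and excluded non-responders do not change the decision.
- The power loss in Case A assumes that excluded patients would respond at 38%. It can fit toxicity holds and early stops of one drug. It does not fit deaths by day 42, which come before the first scheduled scan at 9 weeks.
- The exposure rule is attached only to the primary endpoint, so ORR by iRECIST might be analysed without it. However, no analysis set is named for that endpoint.
- The statistical row of the synopsis is cut off in the text available, and 17.1 does not expressly forbid replacement. Sections 2.0, 17.1 and 17.2 are complete and do not provide for it.

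A pre-specified evaluable set can be a legitimate choice in a single-arm activity trial. The difficulty here is that the set does not match the denominators of the design.

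**Conclusion.** The concern holds. The exposure rule selects patients after baseline, and the plan ties fixed count cutoffs to 13 and 29 without ensuring that many evaluable patients. The design arithmetic in 17.1 is correct; the fault is the mismatch between that design and the analysis set in 17.2.

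The size depends on an exclusion rate that the documents do not give, and the direction depends on who is excluded and whether they are replaced. As written, the consequence is a loss of power (Case A), an overstated response rate (Case B), or a mixture of the two. Inflation of type I error needs replacement, which the plan does not state, together with a response rate below 20% among those excluded. The change is worth making because it is cheap and removes an ambiguity that would otherwise have to be settled after responses are known: 18.2 has responses reviewed at least monthly. Confidence is medium, mainly because the exclusion rate is assumed.

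**What to change.** Amend 17.2 so that:

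1. the primary ORR denominator is all patients who received study treatment, and the same patients form the counts at both Simon looks (13 and 29);
2. a treated patient without a documented response is counted as a non-responder;
3. the set with more than 42 days of concurrent treatment is reported as a sensitivity analysis.

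This keeps the cutoffs of 2 and 9 and the stated operating characteristics: type I error 0.0999 at a true all-treated ORR of 20% and power 0.804 at 38%. It needs no extra patients and only a wording change. The cost is a possibly slightly lower reported ORR and, if 38% was meant for evaluable patients, the lower power given above (0.76, 0.67 or 0.56). Those figures are close to Case A (0.77, 0.69, 0.59). The small difference arises because one calculation fixes the number excluded and the other spreads the dilution over all 29 patients.

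Replacing under-exposed patients would be a poorer remedy: it would restore the numbers but leave the selection in place.

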4.3 Exploratory endpoints

Exploratory biomarkers will be assessed using archival tumor tissue or pre-treatment fresh tumor biopsy (if available) and peripheral blood and correlated with tumor response. Tumor tissue will be assessed by multiplex immunohistochemistry (IHC) assay for intratumoral immune cell subsets and distribution, RNA sequencing (NanoString) for immune gene expression, and T cell receptor (TCR) clonality. The expression levels of biomarkers including c-MET, PD-L1 and PD-L2 in tumor cells and cells of the tumor microenvironment will also be assessed by IHC. Blood-based biomarkers will be explored, including circulating T cell subsets and cytokines.

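### Section 17.2 relates graded biomarkers to ORR, in effect responder yes/no; best percent change in tumour size should be added as a named second outcome

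*Combined protocol and SAP*

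**What the plan says.** The exploratory paragraph of section 17.2 covers four families of marker. It states that the association of immune-cell, marker, gene-signature or "cytokine level with ORR will be evaluated using Spearman correlation", "where $p<0.05$ is considered significant". It gives no effect size, no power and no sidedness, and it does not say what value of ORR each patient contributes.

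Other sections describe the outcome more loosely. Section 4.3 has markers assessed in tissue and "peripheral blood and correlated with tumor response". Section 15.2 refers to response to treatment, section 15.3 to tumor response and section 15.4 to treatment outcomes.

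On the tumour side, the definitions under section 13.1.2 set partial response of target lesions as "At least a 30% decrease in the sum target lesions, taking as reference the baseline sum diameters". The overall-response table in section 13.1.3 then combines target lesions, non-target lesions and new lesions, and any new lesion makes the result progressive disease. Section 17.2 also says that "ORR will also be represented by a waterfall plot", without naming the plotted quantity.

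**The concern.** ORR is a group rate. The only value of it that one patient carries is CR/PR yes or no. Spearman correlation is built for graded data. Given a two-level outcome, it ties all responders with one another and all non-responders with one another. As far as target lesions go, a 29% decrease then counts the same as early growth, and a 31% decrease the same as complete disappearance.

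The graded quantity is already in hand. Measurable disease is required at entry (section 5.1), scans are repeated every 9 weeks on treatment (section 11.2), and a central radiology team reads response (section 13.0). Percent change in the target-lesion sum follows from the same measurements that decide PR. The 30% cut serves the primary endpoint, and nothing in sections 4.3 or 15.2 to 15.4 requires it for the marker analysis.

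At stake is the chance of detecting a real marker association with 29 patients at most. The point is separate from multiplicity and would stand with a single marker.

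**Working it through.** **The plan's own figures.** The documents state no power for the marker analysis, so there is nothing to reproduce there. The primary design does reproduce. It stops at 2 or fewer responders of 13 and rejects at 9 or more of 29. The sum over x from 3 to 13 of P(X1 = x; 13, p) × P(X2 ≥ 9 − x; 16, p) is 0.0999 at p = 0.20 and 0.804 at p = 0.38, against the stated 0.10 and 80%. The point does not touch that design.

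**Inputs from the documents.**
- Maximum n is 29 (section 17.1: "16 additional patients will be accrued for a total of 29 patients").
- The design ORRs are 20% and 38% (section 17.1: "the null hypothesis that the true ORR is 20% will be tested against a one-sided alternative", with 38% as the assumed true rate).
- The level is 0.05 per test (section 17.2).

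**Assumptions, not in the documents.** The test is two-sided. Marker and shrinkage are bivariate normal with correlation rho from 0.3 to 0.6. A responder is a patient whose shrinkage exceeds the cut that gives the stated ORR.

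**Step 1: attenuation.** Cutting a normal outcome at proportion p multiplies its Pearson correlation with the marker by φ(z) / √(p(1 − p)), where z is the normal quantile at the cut. This gives 0.784 at p = 0.38 and 0.700 at p = 0.20. About a fifth to a third of the correlation is lost, and more when responders are few.

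**Step 2: power when the marker tracks depth of shrinkage.** Simulation, 40,000 trials per cell, Spearman test, n = 29. The Monte Carlo standard error of a difference is at most about 0.35 points, and losses were taken before rounding.

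| rho | ORR 38%: percent change vs yes/no | loss | ORR 20%: percent change vs yes/no | loss |
|---|---|---|---|---|
| 0.3 | 32.2% vs 22.6% | 9.6 | 32.2% vs 18.3% | 14.0 |
| 0.4 | 53.1% vs 37.3% | 15.8 | 53.2% vs 29.7% | 23.5 |
| 0.5 | 75.1% vs 55.9% | 19.2 | 75.8% vs 45.6% | 30.2 |
| 0.6 | 91.7% vs 75.0% | 16.7 | 91.3% vs 62.0% | 29.3 |

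With upper ends rounded up, the loss is about 10 to 20 points at 38% and 14 to 31 at 20%. At the rejection threshold, 9/29 = 31%, it is 11.1 to 22.5 points. The rho range is itself a choice: at rho 0.7 and ORR 38% the loss is 8.3 points. With rho = 0 and ORR 38%, both versions reject 5.1% of the time.

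**Step 3: fewer patients.** Archival tissue is collected only if available and biopsy is optional (section 15.1). The trial may also stop at 13 patients. At n = 20 and ORR 38%, the loss over rho 0.3 to 0.6 is 6.0 to 19.5 points. At n = 13 it is 4.1 to 18.2.

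**Step 4: the opposite model.** Suppose the marker mean is shifted by d SD in responders and is unrelated to depth within each group. Shrinkage is taken as uniform from 30% to 70% in responders and from −20% to 30% in the rest. With n = 29 and ORR 38%:

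| d (SD) | percent change vs yes/no | gain for yes/no |
|---|---|---|
| 0.6 | 22.3% vs 30.7% | 8.4 |
| 0.8 | 34.8% vs 48.5% | 13.6 |
| 1.0 | 49.3% vs 66.6% | 17.3 |
| 1.2 | 63.2% vs 81.4% | 18.2 |

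The yes/no outcome now has about 8 to 19 points more power. At ORR 20% the gain is 8.6 to 29.9 points.

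**Step 5: missing scans.** Let 3 of 29 patients have no post-baseline scan, left out of the percent-change test and counted as non-responders in the other. At rho 0.5 and ORR 38%, power is 70.3% against 47.9%.

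**The case against.** The strongest reply is that the plan may not intend a yes/no outcome. Section 17.2 ties ORR to a waterfall plot, which normally shows each patient's percent change, and it chooses a method suited to graded data. The authors may mean percent change, or an ordered CR/PR/SD/PD scale. This cannot be ruled out. What survives is that the outcome variable is undefined, and naming it settles the matter under either reading.

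The second reply is that responder status is more than a cut on target-lesion shrinkage. Under section 13.1.3 it also reflects non-target and new lesions, which percent change ignores. Step 2 builds response purely as a cut of the graded variable, so the graded test has to win there. This stands, and Step 4 shows that the direction can reverse.

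Third, the first on-treatment scan falls at about 9 weeks. Patients who die or progress clinically before it have no percent change, and they matter for a predictive-marker objective. This also stands. Giving such patients the worst rank is not a free remedy: if 15% receive it for reasons unrelated to the marker, the gain at rho 0.5 and ORR 38% falls to about 0 to 2 points.

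Finally, Spearman correlation with a two-level variable is valid, as the 5.1% rejection rate shows, and relating markers to objective response is a legitimate choice. This is agreed. The point concerns information left unused.

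**Conclusion.** The point holds as a minor improvement to the specification and efficiency of an exploratory analysis. On the natural reading, section 17.2 uses only responder status and leaves aside a graded measure that the trial will already have. The loss of about 10 to 20 points at ORR 38%, or 14 to 31 at ORR 20%, applies if the marker tracks depth of shrinkage with rho 0.3 to 0.6 at n = 29. It becomes a gain for yes/no of about 8 to 19 points at ORR 38% if the marker separates only the two response classes.

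A reader might infer three stronger things that the documents do not support:
- That the plan simply forfeits 10 to 20 points of power. No rho is given, 29 is a ceiling, and the sign depends on an unknown relation.
- That percent change should replace objective response. Responder status carries new-lesion and non-target information and keeps patients without a later scan.
- That the waterfall plot already commits the trial to best percent change. The plotted variable is not named. That percent change can be derived rests on the RECIST measurements instead.

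**What to change.** In section 17.2, state that each marker's association with objective response (CR/PR yes or no) will be reported. Add, as a second outcome named in advance, the Spearman correlation of each marker with best percent change from baseline in the sum of target-lesion diameters (central RECIST v1.1 read), in patients with at least one post-baseline scan. Label both as exploratory and report both whatever they show. Any power figure quoted should carry its assumed ORR and rho.

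The cost is a sentence or two of text, with no new scans, samples or patients and no change to the primary endpoint or the two-stage design. The downsides are one more exploratory test per marker, in a plan that states no multiplicity rule, and a second outcome that ignores new and non-target lesions and omits patients without a post-baseline scan. The responder association stays for that reason.

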15.2 Immunohistochemistry (IHC)

Archival or fresh tumor tissue will be immunophenotyped by a comprehensive multiplex IHC assay in the Immunopathology Core at Fred Hutchinson Cancer Center in order to detect a range of immune cell subsets and their distribution in tumor, including CD8+ and CD4+ effector T cells, regulatory T cells, macrophages, myeloid derived suppressor cells.

In addition, IHC will also be performed to assess the intratumoral levels of MET and various markers of immune checkpoint pathways (e.g. PD-1/PD-L1/PD-L2, CTLA-4, LAG3, TIM3). The intratumoral immune profile will be characterized and correlated with response to treatment.

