15.4 Flow cytometry and cytokine assays

Peripheral blood (at baseline, Cycle 1 Day 8, Cycle 2 Day 1) will be analyzed by flow cytometry for immune cell subpopulations (e.g. CD8+/CD4+/regulatory T cells, myeloid derived suppressor cells). Furthermore, serum at the same timepoints will be assayed by the Luminex® cytokine panel. Changes in immune cell subsets and cytokine profiles in response to cabozantinib and pembrolizumab will be assessed and correlated with treatment outcomes.

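### Section 17.2 labels any exploratory marker with an unadjusted Spearman p below 0.05 as significant, over an open-ended set of tests with no multiplicity control

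*Combined protocol and SAP*

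**What the plan says.** The operative rule is the last sentence of Section 17.2: marker "level with ORR will be evaluated using Spearman correlation, where $p<0.05$ is considered significant". It covers four classes of marker and gives neither a number of tests nor an adjustment.

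The range of markers is set out elsewhere:
- Section 4.3, tumor: "The expression levels of biomarkers including c-MET, PD-L1 and PD-L2 in tumor cells", together with gene expression and T cell receptor clonality.
- Section 4.3, blood: "Blood-based biomarkers will be explored, including circulating T cell subsets and cytokines".
- Section 15.2 gives the tumor immune-cell subsets, "including CD8+ and CD4+ effector T cells, regulatory T cells, macrophages, myeloid derived suppressor cells", and MET with six checkpoint proteins as examples.
- Section 15.3 adds two example signatures, pathways and mutations.
- Section 15.4 measures "immune cell subpopulations (e.g. CD8+/CD4+/regulatory T cells, myeloid derived suppressor cells" and a cytokine panel of unstated size, both at three timepoints.

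On the outcome side, Section 4.3 says markers are "correlated with tumor response". Section 17.2 also plans a graphical display: "ORR will also be represented by a waterfall plot".

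**The concern.** A threshold of 0.05 holds the false-positive rate for one test. Applied to dozens of markers in at most 29 patients, it will often produce a significant marker when nothing is there, and a reader of the report could not tell that marker from a real one. The label could then steer later biomarker work.

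A smaller difficulty is that ORR is a group proportion, whereas Spearman correlation needs one value per patient. The plan should say which value that is, because choosing among candidates after seeing the data adds uncounted tests.

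**Working it through.** **1. The plan's own figures.** None is given for the biomarker analysis. The neighbouring ones reproduce. The design in Section 17.1 (stop at 2 or fewer of 13, success at 9 or more of 29) has exact type I error 0.0999 and power 0.804, against the stated 0.10 and 80%. The toxicity statement in Section 17.2 is 1 − 0.95^29 = 0.774, stated as 77%. The same formula, with m tests in place of 29 patients, measures the present problem.

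**2. Counting tests.** The documents give no count, so a range is needed.
- 11: five tumor immune-cell types (15.2), c-MET, PD-L1 and PD-L2 (4.3), and one each of circulating subset, signature and cytokine. 5 + 3 + 3 = 11.
- 18: with the named examples, 12 immunohistochemistry markers (5 + 7), 2 signatures and 4 flow subsets at baseline. No cytokines.
- 26: as 18, with flow at three timepoints. 12 + 2 + 12 = 26.
- 57 and 147: 26 plus T cell receptor clonality = 27, plus an assumed 10 or 40 cytokines at three timepoints (27 + 30; 27 + 120).

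**3. Present rule when no marker is real.** Expected false positives are 0.05m. The chance of at least one is 1 − 0.95^m if tests are independent. The last column is simulated with two-sided tests on yes/no response, n = 29 and equally correlated markers (9 responders for the first three rows, 11 for the last two).

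| m | 0.05m | Independent | Marker correlation 0.5 |
|---|---|---|---|
| 11 | 0.55 | 43% | 31% |
| 18 | 0.90 | 60% | 41% |
| 26 | 1.30 | 74% | 50% |
| 57 | 2.85 | 95% | 69% |
| 147 | 7.35 | >99% | 89% |

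Simulating the independent case gives 42%, 60% and 74% for the first three rows.

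**4. With Benjamini-Hochberg at 10%.** For 11, 18 and 26 markers, each tested against both yes/no response and percent change in one family, the all-null chance of any flagged marker is 10%, 10% and 11% (independent) or 9% throughout (correlation 0.5). On yes/no response alone it is 12% and 15% for 57 and 147 independent tests, and 9% for both at correlation 0.5.

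**5. Power for one true marker.** Assumptions: latent correlation 0.5 with tumor shrinkage, n = 29, 9 responders, other markers null and independent.

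| Rule | 11 markers | 26 markers |
|---|---|---|
| Unadjusted, yes/no | about 52% | about 52% |
| BH 10%, yes/no only | 28–30% | 18% |
| BH 10%, yes/no plus percent change | about 46% | about 35% |

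The last row treats percent change as exactly the quantity that determines response. If 30% of its variance is unrelated noise, the row becomes 36% and 27%. Without that noise, a cytokine panel in the same family lowers it to about 27% at 57 markers and 19–21% at 147. Unadjusted power on percent change alone is about 76% under the same idealised assumption.

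**6. The response variable.** Section 4.1 defines the primary endpoint per patient as complete or partial response by RECIST v1.1, and Section 17.1 glosses tumor response the same way. Section 4.2 defines a second version by iRECIST. Section 15.2 refers to response to treatment, and Section 15.4 to outcomes of treatment without defining them. Section 17.2 does not say which of these enters the correlation.

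**The case against.** The strongest reply is that this work is labelled exploratory in Sections 3.3, 4.3 and 17.2, and that no stopping rule or efficacy claim depends on it. That is correct and limits the weight of the point. It would fully answer a plan that reported associations descriptively, but this plan sets a threshold and attaches the word significant to it.

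Three stronger readings are tempting and are not supported.
- A reader might infer that the response variable is wholly undefined, or could equally be an ordered scale from complete response to progression. Section 13.1.3 does define a per-patient best response: "The best overall response is the best response recorded from the start of the treatment until disease progression/recurrence". But Sections 4.1 and 17.1 make responder yes/no the natural meaning, and no sentence calls for an ordered scale in this analysis. What remains open is RECIST v1.1 versus iRECIST and the looser wording of Section 15.4.
- A reader might infer that one false-discovery family over every platform is the only remedy. It is one option, and costly at 29 patients or fewer. A short primary list with the rest descriptive also answers the point.
- A reader might infer that adjustment costs little power. That comparison credits the adjustment with the gain from adding a second, more informative outcome. On yes/no response alone the loss is about 22–24 points at 11 tests and 34 at 26.

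**Conclusion.** The point holds as a minor one. Followed as written, the rule gives roughly a 42–74% chance of at least one falsely significant marker for 11–26 independent tests, and about 31–50% at marker correlation 0.5. Those counts leave out most or all of the cytokine panel, so they are not upper limits: at an assumed 57 tests the chance is about 95% or 69%.

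The sizes rest on assumed test counts, an assumed correlation structure and all 29 patients contributing. Tissue numbers may be lower, since Section 15.1 makes fresh biopsy optional. The direction does not depend on these choices. The primary endpoint, the two-stage rule and the safety analysis are untouched.

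**What to change.** In Section 17.2:
1. Fix the list of marker-by-timepoint tests before any marker is analysed against response.
2. Remove the bare 0.05 significance rule. Report effect sizes with confidence intervals, unadjusted p-values and Benjamini-Hochberg q-values (for example at 10%), described as hypothesis-generating.
3. Define the family: either all listed tests, or a short primary list such as c-MET, PD-L1 and PD-L2 with everything else descriptive. For three independent tests the unadjusted all-null chance is already only 1 − 0.95^3 = 14%.
4. Name responder yes/no by RECIST v1.1 as the response variable, and bring Section 15.4 into line.
5. Add Spearman correlation with best percent change in the target-lesion sum, which a waterfall plot ordinarily needs anyway. Keep yes/no response beside it, because percent change misses new lesions and non-target progression.

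The cost is a few sentences of text and a short extra analysis, with no new data. The real price is fewer flagged markers, by the amounts in step 5 of the working, and the price rises with the size of the family. That is why the unadjusted results should stay in the report.
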